## 8.0 Radiotherapy

#### 8.1. Dose prescription

The dose prescription is 40 Gy in 15 fractions; treating each field daily. The dose is prescribed to the reference point to which the dose distribution is normalised.

## 9.0 Radiotherapy Target Volumes, Localisation and Outlining

The following borders are marked on the patient's skin prior to the Computerised Tomography (CT) planning scan:

Medial border:	Positioned about the midline, covering palpable breast tissue with a margin not less than 1cm.
Lateral border:	Positioned on the skin parallel to the medial field, approximately mid- axillary line, with a margin not less than 1cm from breast tissue keeping lung volume within tolerance.
Inferior border:	1 cm below inframammary fold or palpable breast tissue.
Superior border:	lower end of sternoclavicular joint or 1 cm above the superior edge of palpable breast tissue avoiding the axilla when an axillary clearance has been performed.

A planning CT scan is performed in the treatment position. Scans are acquired with contiguous 2.5 mm slices.

#### 9.1 Target Volume Definition

The breast 3D PTV contour is field based with negative (inner) margins of:

- 1cm inside the superior and inferior field edges
- 0.5cm inside the patient surface
- 0.5cm from the lung/tissue interface
- 0.5cm inside the field back border -

#### 9.2 Patient Position

Patients lie in a supine position, inclined on a breast board (usually with both arms abducted above the head and gripping poles and cup rests to support the raised arms). Additional devices such as footrests, knee rests, etc., may be used to ensure patient comfort and compliance with positioning. Positional aids marked on the patient (tattoos) or on the support bra are used to ensure patients are in a reproducible position longitudinally with minimal lateral rotation.

A central positioning line, chosen mid way between the SSN and Xiphi-sternum should be marked on the anterior aspect of the bra in the midline, and also on the lateral bra wings using an indelible marker pen, a further vertical laser positioning mark will also be chosen (and marked) on right and left sides at this point. All of the bra settings (points 2 and 12 on the diagram in Appendix 3) are recorded on the patient radiotherapy data sheet and in the patient held Support 4 All pack (see Appendix 6). The inflation levels (ipsilateral and contralateral), and measurements from the SSN to the top of the bra, and the xiphi-sternum to the bottom edge of the bra should be recorded on the patient radiotherapy set up record held by the radiographers. The longitudinal position of the central laser in relation to the breast board scale should be recorded for the purpose of couch/breast board indexing. Following the planning scan the inflated bladders are released and the patient removed from the bed.

The patient may go home in the bra as it is now fitted and the patient should be instructed to avoid changing any of the bra settings when removing the bra at home. The bra can be taken off (and replaced for the first treatment) using the anterior/front fasteners. The patient should be given instructions to wear the bra for the first and subsequent radiotherapy procedures.

#### 9.3 Acquisition of Outlines

A field-based target volume is to be used for treatment planning. (As such the target volume is not a PTV as defined by ICRU 50, but is treated as such for the purposes of dose reporting and referred to as the PTV henceforth.) In order to generate the initial fields on which the resultant target volume is based, the following borders of the palpable breast tissue are marked on the patient's skin prior to the CT planning scan:

#### Table 3 Fields marked at CT Planning session.

Field Border	Description
Medial	Positioned about the midline, covering palpable breast tissue with a margin not less than 1cm.
Lateral	Positioned on the skin parallel to the medial field, approximately mid- axillary line, with a margin not less than 1cm from breast tissue the lateral field border may be adjusted to remain within lung volume tolerance.
Inferior	1 cm below inframammary fold or palpable breast tissue.
Superior	Lower end of sternoclavicular joint or 1 cm above the superior edge of palpable breast tissue avoiding the axilla when an axillary clearance has been performed.

A planning CT scan is performed in the treatment position with a slice thickness of no more than 2.5 mm. The scan must extend to cover the entire ipsilateral lung, as well as a margin of 2 cm around the superior and inferior borders as defined above.

## **10.0 Radiotherapy Planning**

## **10.1 Whole Breast**

The final dose calculation must be performed with correction for tissue heterogeneity, using a Type B algorithm.

The PTV is planned using a pair of isocentric (SAD 100 cm) tangential fields with a non-divergent back edge. The isocentre can be placed on the slice that falls in the centre of the PTV and should be positioned approximately halfway between the posterior border and the anterior surface of the breast. The fields are angled to produce the non-divergent posterior border.

The fields are positioned to cover the PTV such that the maximum depth of lung in the field (defined as the perpendicular distance from the chest wall to the posterior field border) does not exceed 2cm and the maximum depth of heart in the fields (defined as the maximum distance between the posterior field border and the external contour of the heart) does not exceed 1cm.

Wedges are used where necessary to optimise the dose distribution (in some instances, a longitudinal wedge may be required). The use of multileaf collimators (MLC) and field-in-field (FiF) is permitted for further optimisation of distributions as deemed necessary.

Inverse-planned IMRT must not be used.

Planning should aim to produce a balanced distribution across the PTV in all three directions. Where uniform coverage cannot be achieved, coverage of the tumour bed by the 95% (38 Gy) isodose should be prioritised.

The treatment plan should be normalised to a clinically relevant reference point, usually the intersection of the fields, located centrally within the PTV.

## 10.2 Dose Constraints for Organs at Risk (OAR)

The Organs at Risk must be contoured prior to commencement of treatment planning.

Heart: The heart should be outlined using a heart outlining atlas guide(34)

Ipsilateral lung: The entire ipsilateral lung must be contoured, ensuring any major vessels and airways are excluded from the structure.

#### 10.3 Beam Energy

Treatment plans are produced for treatment using photon energies according to local practice. This will normally be 4 – 6 MV, although higher energies (10-12 MV) may be used to provide dosimetric improvements (for example, in fields with a larger separation). The use of mixed energies within a plan should be avoided unless the dose requirements in sections 11.3 and 11.4 cannot be met using the techniques described above.

#### 10.4 Bolus

No bolus should be applied to the skin.

#### **10.5 Dose Limits**

The PTV dose limits are defined in Table 4 below.

#### **Table 4 Dose Limits**

Parameter	Mandatory Dose limit	Optimal limits		
Maximum point dose	< 44 Gy, D max <110% V 105% < 7% V 107% <2%	V105%≤5%		
Minimum dose	V 95% ≥90%	V 95% ≥95%		

#### **10.6 Dose Constraints for Organs at Risk**

Treatment planning should aim to meet the OAR dose constraints defined in Table 5 below.

#### Table 5 Dose constraints to Organs at Risk

	OAR	Dose constraint Optimal	Mandatory
Radiotherapy to left or right breast	Ipsilateral lung	V 30% ≤ 15%	V 30% ≤17%
Radiotherapy to left breast only	Heart		V 25% ≤ 5% V 5% ≤ 30%

#### **10.7 Radiotherapy Planning Data**

Dose-volume histograms (DVHs) are generated for the PTV, ipsilateral lung and heart.

The parameters in Table 6 below should be recorded.

The parameters used to produce the optimum plan will be recorded for each participant (and for each plan produced comparing S4A bra and no bra scans for those women randomised to the intervention arm).

Table 6 Radiotherapy Planning data Recorded for each Patient.

	Structure	Parameter		
Radiotherapy to left or right	PTV	Maximum point dose		
breast		V42.8 Gy		
		V 42 Gy		
		V 38 Gy		
	Ipsilateral lung	V 12 Gy		
		Mean dose		
	Combined lungs	Total combined mean lung dose		
Radiotherapy to left breast only	Heart	V 10Gy		
		V 2Gy		
		Mean dose		
Planning information				
Beam energy required				
Number of fields required				
Time to achieve acceptable plan				
Ease/difficulty of planning score (1 to 3)	2=standard, 1=easier & 3=more difficult			

## **11.0 Treatment Scheduling**

Patients should be treated daily Monday to Friday with no gaps (these patients are considered a category 2 patient), to deliver 40Gy in 15fractions to breast tissue.

## **12.0 Treatment Verification**

Verification of the treatment fields is achieved using 2D megavoltage imaging in conjunction with radiographer assessment of the field coverage on the skin surface/bra surface in comparison with a 3D rendered image of the patient produced from the planning CT dataset. The megavoltage image is a pre-treatment beam portal image allowing assessment of central lung depth, lung symmetry and breast contour.

## **12.1 Treatment Set-up Verification Breast**

The verification procedure outlined above is undertaken on fractions 1-3, then weekly, throughout the treatment course for the purposes of assessment of random and systematic error. All patients in the S4A study will have an image taken daily throughout the treatment course to reassure regarding breast positioning. The impact of the additional imaging is explained below:

- The effective dose from a single lateral portal image of 1 MU at 6MV is 0.6 mSv (Harrison et al BJR 2007 DOI: 10.1259/bjr/32814323). Where Sv represents Sievert (the SI unit for radiation absorption), 1Sv is roughly equivalent in biological effectiveness to 1Gy (1Gy is roughly equivalent to1000mSv). The maximum organ dose for 1 MU at 6MV is approximately 10 mGy.
- Five portal images received by patienrs not in the study will result in approximately 3mSv, fifteen portal images received by study patients will result in approximately 9mSv.

• The reported doses are for the particular patient model used in the reference quoted above, for the size of patient in the S4A study, there may be differences from the values quoted above.

All images are taken and assessed prior to treatment and a cine type time lapse image is taken on fraction 2 to provide additional information with regard to breathing motion. For purposes of assessing random and systematic error images from day 1 to 3 and then a weekly image will be used for both control and S4A intervention arms. The systematic error is calculated using the dataset from the first three images and adjustments made on fraction 4. On the first fraction the set-up is verified by the team of treating radiographers but also utilising the additional skills of the advanced practitioner in breast radiotherapy. Thereafter, images are reviewed online by the senior radiographer and further verified offline by a radiographer trained in portal image assessment. Tolerances used are 0.5cm on the central lung depth.

Measurements as determined by the OnTarget documentation will be recorded and assessed using the verification images as shown in Figure 1 below.

[figure not shown]

Figure 1 Measurement Parameters taken from on-treatment imaging.

- 1 CLD- Central Lung Distance
- 2 CrLD- Cranial Lung Distance
- 3 CBESD Central Beam Edge Skin Distance
- 4 CIW Central Irradiated Width
- 5 CCD Cranio-Caudal Distance

## **13.0 Radiotherapy Quality Assurance**

Planning technicians will contour the heart and lungs as per existing protocol, with these checked by the prescribing Clinician. For quality assurance a second check of contouring by a second Clinician will be undertaken on the first five patients of each trial arm (ten patients in total). A second physics check of the treatment plan on these first ten cases will also be undertaken to enhance study QA.

#### 13.1 Support Bra Use- Fidelity Checks

As the main focus of this study is the introduction of a support bra it is vital that the support bra is fitted and used in the manner that it is intended. Staff at the Host Institution will be trained in fitting and use of the Support 4 All bra. However, it is also important that during the conduct of the trial bra fidelity (ie how accurately the bra is fitted and how faithfully the therapy radiographers, dosimetrists/physicists and patients stick to the guidelines on its use) is assessed and there is not drift over time in how accurately staff implement the bra intervention. Fidelity assessment will be undertaken at random time points during the period of the trial, at times unknown to the treatment staff (but negotiated in advance with the department management team) to ensure accurate assessment of fidelity. We will aim to independently assess the fidelity of at least 12 cases (approximately 25% of the trial sample). An example fidelity checklist can be found in Appendix 4. In addition, the fidelity checking sessions will provide the observers with the opportunity to observe and discuss any challenges the radiographers experience while using the bra across a range of different patient sizes.

## **15.0 Serious Adverse Event Reporting**

#### **15.1 Definitions**

**Adverse Event**: any untoward medical occurrence in a patient or clinical trial subject administered a research procedure. Events may not necessarily have a causal relationship with the procedure.

**Related Adverse Event**: an adverse event assessed by the Principal Investigator or Chief Investigator as reasonably likely to be related to the administration of the research **Serious Adverse Event:** any adverse event or adverse reaction that results in death, is lifethreatening, requires hospitalisation or prolongation of existing hospitalisation, results in persistent or significant disability or incapacity, or is a congenital anomaly or birth defect. The following summaries will be presented: the number and percentages of patients reported as having Serious Adverse Events (SAE) in each treatment arm; as well its associated 95% confidence interval for the estimate (Altman et al 2000); the number and percentages recorded as having all forms of Adverse Events (AE) in each arm; this will be presented as overall and stratified by AE classification .As well as the difference in adverse event rates between each treatment arm and its associated 95% confidence interval for the difference(35).

#### **15.2 Reporting Serious Adverse Events**

These will be reported on S4A serious adverse events (SAE) case report form.

All SAEs should be reported within 24 hours of the investigator becoming aware of the event, by completing the S4A SAE form. The SAE form must be completed, signed and dated by the Principal Investigator or nominated person identified on the delegation log.

The lead Clinicians ([name] or [name]) will review all SAEs to assess relatedness and expectedness. Any relevant follow up information, including any resolution of the event, should be completed on the original S4A SAE form and reported in line with Sheffield Teaching Hospitals standard reporting procedure.

The SAE log should be completed and the SAE form filed in the Site File.

#### 15.3 Reporting Related and Unexpected Serious Adverse events

If a SAE is defined as related and unexpected by the lead Clinicians ([name] or [name]), the CI ([name]) will report the SAE to the main REC within 15 days from the date the event was first reported.

## **16.0 Health Economics Assessment**

This is a feasibility study; therefore economic evaluation will be exploratory in nature. We will employ a cost-effectiveness analysis (CEA) approach to make an assessment of economic impact of using the prototype bra. The main economic endpoints to be measured across both intervention and control cohorts will be:

- 1) Measure of time savings (or time increases) of NHS staff associated with using the bra
- Time taken for the CT radiotherapy planning session.
- Time taken for the radiotherapy dosimetry planning.
- Time taken for each treatment session.
- The number of extra or repeated on treatment imaging exposures.
- Additional time required to re-plan any cases.
- 2) Measure of patient outcomes
- Calculated dose to organs at risk (including mean heart dose for patients treated for a left breast cancer, and mean ipsilateral lung dose).
- Treatment accuracy (random and systematic errors).

The two groups (standard no immobilization versus bra for immobilization) will be compared to estimate the incremental cost-effectiveness ratio. The relevant costs of services and cost savings (potential benefits) to the NHS will be derived from the reference costs provided by the Department of Health and Personal Social Service Research Unit (PSSRU). All costing will be expressed in British pound sterling and no discounting will be used as the study is conducted for a short period.

The data collected will be used to calculate the benefits achievable from the support bra balanced against the potential cost to the NHS for the purchase and use of the product in normal practice.

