#### 7.2 Plan acceptability

Patients randomised to receive the intervention (the S4A bra) will have two CT planning scans (one with and one without the S4A bra). Each scan will be planned as normal but patients will only be treated using the plan with the patient wearing the S4A bra. Both scans will be compared using the following parameters:

- Time taken to achieve an acceptable plan
- Beam energy required to achieve an acceptable plan
- Comparison of dose volume histograms for Planning Target Volume (PTV), lungs and heart (for women planned for a left sided breast cancer).
- Dose to organs at risk, lungs and heart mean doses (see section 7.5 for specific dose measurements to be recorded).

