# Table 2 The Research Questions and the associated outcome measures proposed for this feasibility trial.

No	Research question	Proposed Assessment Method
1	Is the design and current functionality of the bra able to fit with current set-up procedures without too much process adaptation?	Interview of staff involved in the planning and treatment of patients using the bra.
2	Does the bra make it easier to produce an acceptable treatment plan?	Those in the intervention arm will undergo two planning CT scans one with and one without the S4A bra. Two radiotherapy treatment plans will be produced for each patient in the intervention arm; the patient will only be treated using the plan with the patient wearing the S4A bra. Plan evaluations will include measures of dose homogeneity across the planning target volume, time taken to plan, complexity of plan and beam energy required to produce the optimal plan.
3	What are the random and systematic errors in breast positioning with the immobilisation support bra compared with a control group with standard immobilisation (no bra)?	Accuracy derived from on-treatment images on days 1-3 and weekly until the end of treatment for five different parameters (see section 12.1).
4	Is accuracy of positioning using the support bra the same across all breast sizes?	Using individual mean random and systematic errors to correlate with breast volume taken from the radiotherapy plan.
5	What are the differences in the dose to organs at risk when the support bra is used compared with no support bra?	Mean lung and mean heart dose compared between bra and no bra cohorts.
6	Does the support bra reduce the	Skin assessments by health care

	incidence of dry/moist desquamation in the inframmary fold	practitioners taken at baseline and weekly during treatment with comments on the skin scoring (using RTOG) in the inframmary fold ie dry/moist desquamation yes/no and duration
7	Is the current inflation bra design appropriate for patients' aesthetic, and comfort needs?	Assessed with comfort assessment tool (using questions derived from Healthy Volunteer study questionnaire analysis and interviews).

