8	Does the support bra provide measureable changes in patient modesty?	Modesty assessed with the Storyboard of the process with and without the bra – participants asked to choose responses that represent their experiences of physical exposure measured after day 1 and repeated in the final week of treatment. Patients in the control arm are given the storyboard without the bra and asked to rate their experience; patients in the intervention arm given the storyboard with the bra and asked to rate their experience. In the final week of treatment participants are given both storyboards and asked to choose their preference.
9	Does the support bra allow measurable changes in feelings of empowerment compared with the standard no immobilisation process?	Measured using the 15-item patient empowerment scale for cancer patients.
10	Are there any treatment related cost savings from using the support bra?	
 
Assessed through the recording of:
 
1. Time taken for the CT radiotherapy planning session.
 
2. Time taken for the radiotherapy dosimetry planning.
 
3. Time taken for each treatment session.
 
4. The number of extra/repeated ontreatment imaging exposures.
 
5. The number of repeat plans required.
 
6. A measure of the grades of staff required undertaking CT planning, dosimetry planning and treatment set-up procedures.
 

11	Are the patient self-reporting tools easy to use and complete?	Compliance with completion, number of correctly completed booklets and comments made in the booklet by patients.

12	Do HCP RTOG scores correlate with the patient-self reporting scores?	Comparison of HCP recorded RTOG scales and patient scores recorded in the patient- held booklet.
----	--	--

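### The economic comparison uses whole CT-session time, which in the bra arm includes an untimed, research-only no-bra scan

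*Protocol*

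**What the plan says.** Section 16.0 introduces its time measures with "The main economic endpoints to be measured across both intervention and control cohorts will be". The first two listed are "Time taken for the CT radiotherapy planning session" and the time for dosimetry planning. It then says: "The two groups (standard no immobilization versus bra for immobilization) will be compared to estimate the incremental cost-effectiveness ratio". The stated purpose is to set benefits against "the potential cost to the NHS for the purchase and use of the product in normal practice". The section also says that the "economic evaluation will be exploratory in nature".

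Table 2, question 10 (treatment-related cost savings) repeats the CT-session item and "Time taken for the radiotherapy dosimetry planning". It also counts repeat plans.

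The arms do not undergo the same planning procedures. Section 7.2 states: "Patients randomised to receive the intervention (the S4A bra) will have two CT planning scans (one with and one without the S4A bra"). Table 2, question 2 adds: "Two radiotherapy treatment plans will be produced for each patient in the intervention arm". Both places say that treatment uses the with-bra plan only. Section 21.0 describes one planning scan as the normal procedure for controls. Its paragraph on burdens says that participants attend nothing beyond their standard radiotherapy appointments.

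**The concern.** The bra arm's no-bra scan exists for the repeated-measures comparison described in section 4.0. A patient given the bra in routine care would not have it. If the whole session is timed in both arms, that scan is counted as though it were a consequence of using the bra.

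The resulting time difference, and any staff cost derived from it, would not measure what section 16.0 sets out to measure, namely cost in normal practice. Research question 10 would be answered with an error in one known direction, and the figure could carry over into the economic design of the definitive trial.

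**Working it through.** **1. Confirm the scan imbalance from the protocol's own dose totals (section 21.0).** Inputs: 7.2 mSv per planning CT; a pre-treatment image of 4 MU at 0.6 mSv/MU.

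- Arm A: 7.2 + 4 × 0.6 = 9.6 mSv (stated: 9.6).
- Arm B: 2 × 7.2 + 4 × 0.6 = 16.8 mSv (stated: 16.8).
- Difference: 16.8 − 9.6 = 7.2 mSv, exactly one CT scan.

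With 25 patients per group (section 5.2), the bra arm has 25 study-only scans and the control arm has none.

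**2. Is the extra scan inside the timed item?** The endpoint is the session, not a scan. Section 21.0 rules out additional appointments, and the assessment matrix shows both scans under a single radiotherapy-planning entry. The natural reading is that both scans fall in one session. Section 16.0, Table 2 and Table 6 contain no per-scan time and no rule excluding the second scan.

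**3. Size of the error.** Let d be the true effect of the bra on session time and s the time added by the no-bra scan. Then

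observed difference = d + s.

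The protocol gives no CT times, so the values of s and d below are assumptions, in minutes:

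| s | observed if d = −5 | observed if d = 0 | observed if d = +5 |
|---|---|---|---|
| 5 | 0 | +5 | +10 |
| 10 | +5 | +10 | +15 |
| 15 | +10 | +15 | +20 |
| 20 | +15 | +20 | +25 |

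The error is s in every cell. Under these assumptions a true 5-minute saving appears as anything from no difference to a 15-minute increase.

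**4. Can it be removed afterwards?** Not from one session time. Part of a longer bra session is a genuine cost of the bra: section 9.2.1 places measuring, fitting and inflation in the same CT session. A single total does not separate that work from the research scan.

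**5. Does the same apply to dosimetry planning?** No. Section 10.7 has planning parameters recorded for each plan, bra and no-bra, and Table 6 includes the time to reach an acceptable plan. Section 7.2 compares that time between the two scans. The with-bra plan time is therefore available for comparison with the control arm's single plan, and using it makes the inflation zero. What is missing is a statement in section 16.0 of which plan's time enters the comparison.

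**The case against.** The strongest reply is that section 16.0 already points to the right quantity. It speaks of staff time associated with using the bra and of cost in normal practice, and a no-bra comparison scan is neither. No text says that the scan is to be charged to the bra, unit costs come from national sources, and the choice of resources to count is commonly left to an analysis plan. The evaluation is exploratory, and no economic result appears among the stop/go criteria in Table 1.

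Much of this stands, and it limits the importance of the point. It does not remove the CT problem. An analysis plan can choose among recorded times, but it cannot divide a session recorded as one number. The remedy has to be in the data collection.

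A reader might also infer that planning time in the bra arm is doubled, so that only a bra that halved planning time would look neutral. The documents do not support this. It would require adding two plan times that are recorded separately, and nothing says to add them.

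**Conclusion.** The point holds for CT-session time. As written, the between-arm difference, and the cost derived from it, is overstated against the bra by the full duration of the no-bra scan. The amount cannot be stated because the protocol gives no times; the 5 to 20 minutes used above is illustrative. The conclusion assumes that both scans take place in the one timed session and that the no-bra scan is not timed apart, which is how the protocol reads.

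For dosimetry planning no bias is built in; section 16.0 only needs to name the plan that counts. Nor do the documents support saying that the economic analysis as a whole is designed to make the bra look costlier: no rule assigns the research procedures to the bra, and the stated target is normal practice.

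Severity is modest, given the exploratory status. The change is still worth making before data collection, because the error runs in one direction, affects a stated research question and may not be recoverable.

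**What to change.** - **CT form:** record the no-bra scan time separately, with defined start and stop points that cover any repositioning done only for that scan.
- **Section 16.0 and Table 2, question 10:** state that the bra arm is costed on the with-bra scan (including measuring, fitting and inflation) and the already recorded with-bra plan time only, against the control arm's single scan and plan.
- **Reporting:** give the research-only scan and plan time separately, outside the cost difference, and do not count the research plan as a repeat plan.

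The cost is one extra time field and a sentence in each of the two places. No new planning-time field is needed.
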